### **ACO Adjudication**

Because the infarct-related artery may spontaneously open by the time of the angiogram or total occlusion may be chronic in nature, we defined a composite ACO using following criteria:

(1) total occlusion or presence of culprit lesion on angiography

PLUS

a peak troponin I level equal to or greater than 1.0 ng/ml

PLUS

at least 20% rise within 24 hours

(2) a highly elevated peak troponin, i.e., peak troponin I > 5.0 ng/mL, which was shown to be highly correlated with ACO

(3) cardiac arrest before any troponin rise has been documented with supporting clinical evidence of possible ACO.

### **Statistical Analysis**

Baseline characteristics will be summarized using standard descriptive statistics. Comparisons of relevant parameters between groups will be performed by chi-square, Fisher's exact test, Mann-Whitney U, Kruskal-Wallis H test, one-way ANOVA and student t-test, as appropriate. Patients with missing values will be excluded pairwise from analyses. A Cohen's  $\kappa$  test will be used for determination of the intra- and inter-observer agreement for ECG classifications.

Kaplan-Meier analysis will be performed to determine the cumulative long-term mortality rates in different ECG subgroups. The mortality across groups will be compared using log-rank test. A Cox-regression model will be used to perform a survival analysis according to intervention timing and revascularization status. Baseline characteristics with a P value of 0.05 or less in the univariate analysis will be included and a step-down procedure will be applied for selection of final covariates.

**Note:** After data collection, we performed a univariate analysis for mortality and found that many of the baseline parameters, including age, systolic blood pressure, heart rate, baseline

creatinine etc., were significantly associated with long-term mortality. But when these were included in the Cox regression analysis alongside with baseline GRACE risk score, they all lost their statistical significance. Considering GRACE risk score already includes almost all of these variables, we only used GRACE risk score as a covariate in Cox regression model.

The sensitivity, specificity and diagnostic accuracy of STE/non-STE or ACO/non-ACO ECG approaches will be calculated using receiver operating characteristics analysis. As these parameters are highly dependent on the pre-test probability of the disease and pre-test probability of ACO and long-term mortality are closely associated with the presentation type, we will also repeat these analyses after weighing cases for the total number of hospital admissions in the study period.

Statistical analyses will be performed with SPSS (version 24.0; SPSS Inc., Chicago, IL) and MedCalc Software (version 18.2.1 [Evaluation version]; MedCalc Software, Ostend, Belgium).

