- NSTEMI group: These patients should have both of the following criteria: (1) a peak troponin level above 99th percentile and (2) a clinical picture compatible with acute coronary syndrome. But these patients should not have STEMI criteria ((1) New ST-segment elevation at the J-point in two contiguous leads with the cut-point:  $\geq 1$  mm in all leads other than leads V2–V3 where the following cut-points apply:  $\geq 2$ mm in men  $\geq 40$  years;  $\geq 2.5$  mm in men  $< 40$  years, or  $\geq 1.5$  mm in women regardless of age).
- Control group: These patients should have (1) a technically adequate ECG, (2) a clinical picture compatible with acute coronary syndrome, (3) a peak troponin level below 99th percentile or, if low-positive, change in the first 12-hours should

be less than 20%.

All of these patients may or may not have undergone catheterization during their hospital stay.

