### **Estimated number of subjects to be submitted:**

We estimated that the enrollment of 963 patients in non-STE-MI group would provide the study with a statistical power of 95% to detect a relative excess mortality rate of 5% in ACO-MI subgroup (from 10% to 15%) with the use of a two-sided test at the 0.05 level, with a frequency prediction of 25% for ACO-MI. Far less patients (267 and 383) would be necessary to detect a 10% difference in area under curve (AUC, from 0.700 to 0.770) for the comparison of diagnostic accuracy two approaches in predicting ACO and long-term mortality, respectively.

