### **4. Data Collection**

- 1) Starting from May 1, 2017 hospital database will be screened for STEMI and NSTEMI admissions.
- 2) Following will be checked:
  - The presence of a technically adequate (pre-cath) ECG.
  - A peak troponin level over 99 th percentile.
- 3) ECGs will be printed and handed over to ECG reviewers after all groups are completed.
- 4) Following baseline variables will be entered to the study Excel spreadsheet:  
Enrollment no., protocol no., cohort, age, gender, prior history of MI, prior history of PCI or CABG, presence or absence of diabetes (medication use or HbA1c>6.5), hypertension (medication use or average blood pressure over 140/90 mmHg during hospital stay), dyslipidemia (medication use), smoking (current smoker or past smoker with in 1 year), admission systolic blood pressure, admission heart rate, admission creatinine level, admission hemoglobin level, Killip class on admission, admission troponin I level (from a blood sample collected before, during or just after coronary angiography or at admission to the emergency department), peak troponin level (the maximum troponin level during hospital stay), 24-to-48 hour troponin level (the highest troponin level during this time window), ejection fraction from echocardiogram report, time from ECG to PCI (will be calculated from system recordings), in-hospital mortality, in-hospital resuscitation, in-hospital intubation.
- 5) From these parameters, baseline GRACE risk score, the change within troponin value in the first 24 hours will be calculated.

- 6) Angiograms will be reviewed by angiogram reviewers from hospital digital database. Following points will be noted: (1) the presence of total occlusion. The presence of collaterals to distal vessel, appearance of the total occlusion, easiness of guidewire crossing will also be assessed to determine if the total occlusion is acute in nature. If necessary, primary operator will also be contacted. (2) The presence of culprit lesion, which was defined based on several angiographic properties including appearance, presence of angiographic thrombus, critical stenosis with less than Thrombolysis in Myocardial Infarction 3 flow.

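### The Cox model by revascularization and its timing states no time zero and no time-dependent coding; a fixed ever/never covariate with the clock started at admission or ECG would favour revascularization.

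*Combined protocol and SAP*

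**What the plan says.** One sentence in Statistical Analysis describes the model: "A Cox-regression model will be used to perform a survival analysis according to intervention timing and revascularization status". The note in the same section gives the adjustment: "we only used GRACE risk score as a covariate in Cox regression model".

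Section 2, Patient selection, shows that the exposures are events of the hospital stay: "All of these patients may or may not have undergone catheterization during their hospital stay". Section 4, Data Collection, requires "The presence of a technically adequate (pre-cath) ECG" and lists "time from ECG to PCI (will be calculated from system recordings), in-hospital mortality" among the variables. So the interval from ECG to PCI is recorded.

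The available text does not give:
- the origin of survival time;
- the categories of timing;
- how patients without PCI enter;
- whether either exposure changes during follow-up.

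The variable list in section 4 has prior PCI or CABG and the ECG-to-PCI time, but no item for revascularization during the index stay. It lists "in-hospital mortality, in-hospital resuscitation, in-hospital intubation" with no date or time of death. One part of the document, between the sample-size paragraph and section 4, was not available for checking.

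**The concern.** A patient has to survive long enough to be revascularized. If the clock starts at admission or ECG and status is fixed as ever/never, the wait is credited to the revascularized group as time in which nobody can die. Deaths during the wait go to the other group. The distortion runs toward apparent protection. A baseline score cannot repair it, because the error lies in how exposure is defined and not in case mix.

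This is the one planned model that relates survival to reperfusion. The Study Project Summary is concerned that patients with an occluded artery labelled non-STEMI miss emergent reperfusion. Those patients are also the likeliest to wait. A hazard ratio below 1 for revascularization could be read as support for that concern when part of it comes from a few early deaths counted in the wrong group.

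**Working it through.** The plan states no figure for this model, so there is none to reproduce. The check asks how far the hazard ratio moves when the procedure truly has no effect.

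**Inputs from the documents** (sample-size paragraph): 963 patients in the non-STE group; mortality 10% and 15%; ACO-MI share "with a frequency prediction of 25% for ACO-MI". Hence:
- the ACO-MI subgroup is 0.25 × 963 = 241 patients, with 15% mortality;
- overall mortality is 0.25 × 15% + 0.75 × 10% = 11.25%.

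**Assumptions not in the documents:** 75% destined for a procedure; exponential waits; 1% to 4% dead by day 7; a two-year horizon; death hazard independent of the procedure.

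**Hand check, n = 963, median wait 24 h, 4% dead by day 7.**
1. Daily death hazard in week one: h = −ln(0.96)/7 = 0.00583. Daily procedure rate: λ = ln 2 = 0.693.
2. Chance of dying before the procedure: h/(h+λ) × (1 − e^(−7(h+λ))) = 0.00834 × 0.9925 = 0.00828.
3. Destined for a procedure: 0.75 × 963 = 722.25. Deaths while waiting: 722.25 × 0.00828 = 6.0.
4. Total deaths: 0.1125 × 963 = 108.3, of which 81.3 are in those destined and 27.1 in the other 240.75.
5. After the six move: 75.3/716.3 = 10.5% against 33.1/246.7 = 13.4%, a ratio of 0.78.

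For n = 241 the same steps move 1.5 deaths: 25.6/179.3 = 14.3% against 10.5/61.8 = 17.1%, a ratio of 0.84.

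**Simulation under the null, ever/never status, clock from ECG** (hazard ratio, with false significance at two-sided 0.05):

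| Median wait | Dead by day 7 | n = 963 | n = 241 |
|---|---|---|---|
| 1.4 h | any | about 1.0 | about 1.0 |
| 12 h | 1% | 0.97 (5%) | 1.02 (5%) |
| 24 h | 1% | 0.94 (6%) | 0.98 (5%) |
| 24 h | 2% | 0.87 (12%) | 0.92 (6%) |
| 24 h | 4% | 0.77 (29%) | 0.83 (11%) |
| 48 h, waits capped at 72 h | 4% | 0.75 to 0.77 (about 25%) | 0.85 (8%) |
| 48 h, uncapped | 4% | 0.63 (64%) | 0.71 (19%) |

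The uncapped bottom row should not be the headline, since it places about 9% of planned procedures after day 7.

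**Alternatives, same null.**
- Time-dependent coding, n = 963: 1.00 to 1.01, false significance 4% to 6%. At n = 241: 1.02 to 1.05 (medians 0.99 to 1.03), so values slightly above 1 there are small-sample skew.
- Ever/never status with the clock started at day 7, as a stand-in for discharge, n = 963: 1.01, false significance 5%.
- Landmark at 24 h, used only as an illustration, n = 963: 0.98 to 1.01.
- Adjusting the ever/never model for a simulated baseline score (24 h, 4%): 0.75 before and 0.75 after at n = 963; 0.83 and 0.82 at n = 241.

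**The case against.** The strongest reply is that the plan never says ever/never, and never says the clock starts at admission. The bias needs both. The plan names in-hospital and long-term mortality separately, so a post-discharge clock is possible, and it would not carry this bias. Timing and status could also form one combined variable, and early treatment against all others is nearly unbiased in the same simulations (0.95 to 0.99). All of this stands. A reader might infer that the planned hazard ratio is biased; the documents support only that it would be under one open reading.

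Three further inferences are tempting and not supported.
- The missing-data rule, "Patients with missing values will be excluded pairwise from analyses", might be read as dropping everyone without PCI from the timing analysis, leaving early against late-treated patients. That contrast would lean the other way (1.03 to 1.17). But a patient who had no PCI has an interval that does not apply, which is not clearly a missing value, and the plan does not say it is treated as one.
- The note on GRACE might be read as showing that this model was already fitted. It describes covariate selection in a Cox regression for mortality, and does not show that timing or status was in it.
- The large distortions might be taken as expected. They depend on assumed waits and early mortality. If instead 40% of deaths are spread over 30 days, the range at n = 963 is only 0.97 to 0.87.

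It is also fair that time-dependent coding leaves confounding by indication. With an unmeasured factor (log hazard ratio 0.3, 0.5 or 0.7 per SD for death, with equal log-odds against a procedure) the time-dependent hazard ratio is 0.93, 0.81 or 0.68 under no true effect. The fix removes one error; it does not make the estimate causal.

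**Conclusion.** The point holds in conditional form. The plan fits a Cox model to two post-admission exposures without the elements that decide whether deaths before a procedure are placed correctly. The recorded ECG-to-PCI time defines the interval, but not the survival origin, the timing categories or the place of untreated patients. With a clock from admission or ECG and fixed ever/never status, the immortal-time component runs toward apparent protection. The net direction is less certain, because confounding may add to it or offset it.

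On the assumptions above, the null hazard ratio is about 1.0 for waits of an hour or two, close to 1 when early mortality is 1% and the wait is a day or less, and about 0.75 to 0.85 for waits of one to two days with 4% dead by day 7. The exposure is therefore mainly in NSTEMI patients with delayed procedures.

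No section makes this model primary or sizes the study on it. The Kaplan-Meier and log-rank comparison by ECG subgroup and the ROC analyses are untouched. This is a worthwhile, cheap improvement to one model, not a challenge to the study's main comparisons.

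**What to change.** 1. Start the clock at the qualifying pre-catheterization ECG, and state this.
2. Enter revascularization as a time-dependent covariate that switches on at the recorded ECG-to-PCI time, and at the CABG date if status includes CABG.
3. For timing categories, use a landmark at the end of whatever window the sponsor defines. Classify patients alive then by what has happened by then, and keep those without PCI as not yet treated.
4. Report deaths before any procedure, separately for STEMI and NSTEMI.
5. Declare the change as made after data collection, and describe the hazard ratio as an association.

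Cost: no new patients. Death times must be retrieved or confirmed, as must any in-hospital CABG dates. If only death dates exist, placing deaths at the end of the day gives 0.93 to 1.00 under the null (n = 963). Switching exposure on from the day after the procedure gives 1.00 to 1.02, but counts procedure-day deaths as unexposed. A landmark drops the earliest deaths and conditions on survival to it: 1% to 5% of deaths at 24 h, and 4/11.25 = 36% at day 7 in the 4% scenario.

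### The Cox comparison by intervention timing and revascularization status is adjusted for GRACE alone, so residual confounding is possible and the plan does not rule it out

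*Combined protocol and SAP*

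**What the plan says.** The Statistical Analysis section states: "A Cox-regression model will be used to perform a survival analysis according to intervention timing and revascularization status". Its covariate rule is: "Baseline characteristics with a P value of 0.05 or less in the univariate analysis will be included and a step-down procedure will be applied".

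A Note in the same section then reports what was done. "After data collection, we performed a univariate analysis for mortality", and "many of the baseline parameters, including age, systolic blood pressure, heart rate, baseline" creatinine and others not named, were associated with long-term mortality. Entered "alongside with baseline GRACE risk score, they all lost their statistical significance". The Note adds a second reason, that the score already contains nearly all of these variables, and concludes that "we only used GRACE risk score as a covariate in Cox regression model".

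Two other sections matter. Section 2 (Patient selection) says that patients in every group could have been catheterized or not, so treatment was not assigned by the study. Section 4 (Data Collection) says that GRACE is calculated from the collected variables. Its list also includes prior MI, prior PCI or CABG, "presence or absence of diabetes (medication use or HbA1c>6.5"), hypertension, smoking, gender and admission hemoglobin.

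**The concern.** Patients who are treated early, or revascularized at all, are selected by their clinicians. A hazard ratio for timing or revascularization is therefore only as good as its adjustment. A variable confounds that comparison if it is related both to treatment and to death, given what is already in the model. The test the Note reports, significance for mortality beside GRACE, looks at only one of those two relations, and does so through a P value that depends on the number of deaths.

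The test is also weak for variables inside the score: a component entered next to a composite built from it is expected to lose significance. For variables outside the score, non-significance does not make omission harmless. By the Note's own wording the score covers nearly all of the mortality-associated variables, so at least one lies outside it and was dropped. It is not named.

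At stake is the reading of the timing and revascularization hazard ratios. A shift from confounding could be taken for benefit or harm of treatment.

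**Working it through.** **No figure to reproduce.** The documents give no hazard ratio, death count, follow-up time or analysis population for the Cox model. The check sets the stated reasons against what they can support, then gives an illustration under assumptions.

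**The two reasons**

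| Stated reason | What it supports | What it does not support |
|---|---|---|
| GRACE covers nearly all of the variables | Not entering components a second time; they are adjusted for through the score | Dropping variables outside the score |
| The others lost significance beside GRACE | No clear added association with death in these data | Absence of confounding of timing or revascularization |

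The documents do not list the GRACE components or say which variables fall outside the score. They report no covariate balance by timing or revascularization, and no change in the treatment hazard ratio when covariates were removed.

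**Illustration of size (all inputs assumed).** Simulated Cox data: 1000 patients, 300 runs per setting, true treatment hazard ratio 1.0, a GRACE-like score related to treatment and death, and one binary confounder outside the score with prevalence 30%. The confounder raises the hazard of death and lowers the odds of treatment. The shift is the treatment hazard ratio from the score-only model divided by that from the model that adds the confounder.

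| Confounder HR for death | Odds ratio with treatment | Score only | Score + confounder | Shift | Confounder non-significant |
|---|---|---|---|---|---|
| 1.25 | 1.5 | 0.975 | 0.994 | 0.981 | 76% |
| 1.25 | 2.5 | 0.951 | 0.994 | 0.957 | 78% |
| 1.5 | 1.5 | 0.965 | 1.005 | 0.960 | 31% |
| 1.5 | 2.5 | 0.913 | 0.986 | 0.926 | 43% |
| 2.0 | 1.5 | 0.946 | 1.008 | 0.938 | 1% |
| 2.0 | 2.5 | 0.855 | 0.982 | 0.871 | 1% |

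For moderate confounders (HR 1.25 to 1.5) the shift is 1 − 0.981 = 1.9% to 1 − 0.926 = 7.4%, and the confounder would often fail a 0.05 test. A confounder with HR 2.0 would seldom fail it at this size and prevalence.

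**Hand check.** Shift ≈ (1 + (HR − 1)·p_treated) / (1 + (HR − 1)·p_untreated), ignoring the score. The treatment probability is 0.5 without the confounder, and 1/(1 + 1.5) = 0.40 or 1/(1 + 2.5) = 0.286 with it. At 30% prevalence:

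- Odds ratio 1.5: p_treated = 0.12/(0.12 + 0.35) = 0.255; p_untreated = 0.18/(0.18 + 0.35) = 0.340. With HR 1.25: 1.064/1.085 = 0.98.
- Odds ratio 2.5: p_treated = 0.0857/(0.0857 + 0.35) = 0.197; p_untreated = 0.2143/(0.2143 + 0.35) = 0.380. With HR 1.5: 1.0985/1.190 = 0.92.

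Both agree with the simulation (0.981 and 0.926).

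**Room for covariates.** The sample-size section gives 963 patients, 25% ACO-MI, and mortality of 15% versus 10%. Expected deaths = 963 × (0.25 × 0.15 + 0.75 × 0.10) = 963 × 0.1125 ≈ 108. At an assumed 10 deaths per term, that allows about 10 terms. If the Cox model is fitted in the NSTEMI group, which the plan does not state, event numbers do not force a single covariate.

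**The case against.** A good deal can be said for the GRACE-only model.

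- *Components of the score are already adjusted for.* This stands. The criticism reaches only variables outside GRACE, and the documents do not let a reader list them.
- *The written rule was data-driven anyway, and the change is disclosed.* Also true: step-down selection could have ended at GRACE alone, so the departure from plan is modest. But selection by P value has the same weakness either way, and disclosure does not show that the estimate is unaffected.
- *Strong confounders would have shown up.* Partly true. An HR of 2.0 was missed in about 1% of runs, against 31% to 78% for an HR of 1.25 to 1.5. The Note does not say which variables were entered, so even this reassurance is limited.
- *This is not the main analysis.* The Study Project Summary asks about identification by ECG, and the study is sized on ACO-MI mortality and AUC. That limits the weight of the point, not its validity.
- *The plan restricts candidates to baseline characteristics, so post-treatment variables are excluded.* This does not stand as written: section 4 lists peak troponin and in-hospital events among its baseline variables.

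A reader might infer that known confounders were left out, or that the hazard ratio is materially wrong. The documents support neither. They identify no variable that differs by treatment, predicts death given GRACE and lies outside the score. A larger bias can be produced by multiplying several assumed strong confounders, but that needs independence and conditional effects that nothing in the plan establishes.

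**Conclusion.** The point holds as one of possible residual confounding that is not ruled out. The comparison is non-randomized, the single-covariate model was settled after mortality associations had been examined, and neither stated reason shows that variables outside GRACE can be omitted safely.

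The likely size is modest: about 2% to 7% on the treatment hazard ratio for each omitted moderate confounder, more if several act in the same direction and less if they offset one another. That range rests on assumed prevalence, effect on death and association with treatment, all conditional on GRACE; none comes from the documents. The direction in the real data is unknown. The weakness is correctable with data already collected and does not invalidate the design.

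**What to change.** Fit one additional Cox model for timing and revascularization status.

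- **Covariates:** GRACE plus collected pre-treatment variables not already in the score, chosen on clinical grounds and not by P value. Candidates are diabetes, prior MI, prior PCI/CABG, hypertension, smoking, sex and admission hemoglobin; leave out any that GRACE already contains.
- **Exclusions:** post-treatment items that section 4 lists as baseline, namely peak troponin and in-hospital events, and ejection fraction unless it was measured before treatment.
- **Reporting:** give this hazard ratio beside the GRACE-only one, label both as specified after the data were seen, and name the variables that GRACE does not cover. If the two differ, limit any conclusion about timing or revascularization.

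No new data are needed. The model costs degrees of freedom: GRACE, seven variables and one term each for timing and revascularization make 1 + 7 + 2 = 10 terms, about all that 108 deaths would allow at 10 per term. It may also lose patients, since the plan excludes those with missing values. Check the number of covariates against the actual deaths in the population analyzed, and shorten the list on clinical grounds if it is too long.

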### **2. Patient selection**

We planned to enroll 1000 patients in each of the STEMI, NSTEMI and control groups.

Considering [name] Thoracic and Cardiovascular Surgery Training and Research Hospital has a large local network for primary with around 1000-1500 STEMI patients per year referred for primary PCI, it will take approximately one-year period to collect 1000 STEMI patients. This institution also receives STEMI and NSTEMI patients with a 2:1 ratio, which corresponds well to the reported incidences of these two entities. Therefore, we expected to enroll 1000 NSTEMI patients before STEMI group is completed. Another 1000 patients with a clinical picture compatible with an acute coronary event, but without any ECG changes during serial follow-up and negative and unchanging troponin levels within the first 24 hours will be enrolled. As these patients were so much in frequency, and this group would be completed at the beginning of the study, if we started at the same time with

STEMI/NSTEMI enrollment (May 1, 2017); we decided to select these patients from a computer-generated random list. Therefore, the patients in these group was enrolled after first two groups were completed (December 31, 2018). The total admission counts will also be calculated for the weighted analysis of diagnostic accuracy indexes; such as sensitivity, specificity, negative and positive predictive value. After this enrollment period we will have three cohorts.

- STEMI group: These patients should have all of the following criteria: (1) New ST-segment elevation at the J-point in two contiguous leads with the cut-point:  $\geq 1$  mm in all leads other than leads V2–V3 where the following cut-points apply:  $\geq 2$  mm in men  $\geq 40$  years;  $\geq 2.5$  mm in men  $< 40$  years, or  $\geq 1.5$  mm in women regardless of age. (2) a peak troponin level above 99th percentile and (3) a clinical picture compatible with acute coronary syndrome.

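### The mortality ROC comparison has no common follow-up horizon, so unequal closing of the STEMI and NSTEMI groups could shift the paired AUC difference by about 0.005–0.017

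*Combined protocol and SAP*

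**What the plan says.** The section on the estimated number of subjects gives 267 and 383 patients to detect an AUC of 0.770 against 0.700 "for the comparison of diagnostic accuracy two approaches in predicting ACO and long-term mortality, respectively". Long-term mortality is therefore a planned ROC outcome, with 383 as its figure.

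The Statistical Analysis section states the method: "The sensitivity, specificity and diagnostic accuracy of STE/non-STE or ACO/non-ACO ECG approaches will be calculated using receiver operating characteristics analysis". That sentence does not name mortality. The next one does, noting that "pre-test probability of ACO and long-term mortality are closely associated with the presentation type" and adding a repeat analysis weighted by hospital admissions. This weighting is the only adjustment, and it does not concern time at risk.

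Earlier in the same section the endpoint is treated as time-to-event: "Kaplan-Meier analysis will be performed to determine the cumulative long-term mortality rates in different ECG subgroups", followed by log-rank and Cox analyses.

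On timing, section 2 (Patient selection) dates the start as "STEMI/NSTEMI enrollment (May 1, 2017" and has the controls "enrolled after first two groups were completed (December 31, 2018". It expects the NSTEMI quota to fill before the STEMI quota. It also gives 1000–1500 STEMI patients per year and a STEMI to NSTEMI ratio of 2:1.

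**The concern.** An ordinary ROC analysis needs a yes/no outcome. If that outcome is death by a common closing date, patients who entered earlier have had longer to die.

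The two ECG approaches agree on type 1a (positive under both) and on types 2–4 (negative under both). They disagree on type 1b, which only the ACO approach calls positive, and on types 1c and 1d, which only the STEMI criteria call positive. By definition type 1b belongs mainly to the NSTEMI cohort and types 1c/1d to the STEMI cohort. If those cohorts are followed for different lengths of time, recorded deaths in the discordant classes differ even when their true hazards are equal. The paired AUC difference then partly reflects the enrolment calendar.

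At stake is the error rate, in both directions, of the comparison of the two approaches for mortality.

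**Working it through.** **The plan's own figure.** The 383 cannot be reproduced from stated inputs: the power for this comparison, the correlation between the two tests and the share of deaths are not given. With the Hanley–McNeil variance for two correlated AUCs and two-sided 0.05, it is reached at 80% power with, for example, r = 0.85 at 11.25% deaths or r = 0.70 at 25% deaths. Neither the figure nor its inputs imply a follow-up time.

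**Do the groups close together?** From section 2:
- STEMI: 1000 patients at 1000–1500 per year takes 8–12 months.
- NSTEMI: the 2:1 ratio gives 500–750 per year, so 1000 patients take 16–24 months.

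The rates imply that STEMI closes first; the text expects NSTEMI first. Either way the closing times differ, but the order is contradictory. MI entry spans 1 May 2017 to 31 December 2018, or 20 months.

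**Assumptions (not in the documents).** 850 type 1a and 150 type 1c/1d in the STEMI cohort; 250 type 1b and 750 others in the NSTEMI cohort; 1000 controls; mortality 8% per year in every class; uniform entry; one closing date at month 26–44. All type 1b patients are placed in the NSTEMI cohort, although some type 1c tracings are reclassified to 1b.

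**Formulas.** For a binary test, AUC = (sensitivity + specificity)/2. Let w = +1 for type 1b, −1 for types 1c/1d and 0 otherwise. Then

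AUC(ACO) − AUC(STE) = ½ [mean w in the dead − mean w in the living].

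For entry uniform on months a to b, closing month c and k = 0.08/12 per month,

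P(dead) = 1 − [exp(−k(c−b)) − exp(−k(c−a))] / [k(b−a)].

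**Closing at month 32.** P(dead) is 15.89% for entry over months 0–12 and 13.58% for months 0–20.

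- All groups 0–20: difference 0.000.
- STEMI 0–12, others 0–20: sum of w in the dead = 250×0.1358 − 150×0.1589 = 10.1, among 430.5 deaths; in the living 89.9 among 2569.5. Difference = ½(0.0235 − 0.0350) = −0.006.
- NSTEMI 0–12, others 0–20: 250×0.1589 − 150×0.1358 = 19.4 among 430.5; 80.6 among 2569.5. Difference = ½(0.0450 − 0.0314) = +0.007.

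**Closing at month 26**, NSTEMI 0–12, STEMI 0–20, controls 20–24. P(dead) is 12.46%, 10.05% and 2.63%. Sum of w = 250×0.1246 − 150×0.1005 = 16.1 among 251.4 deaths; 83.9 among 2748.6 living. Difference = ½(0.0639 − 0.0305) = +0.017.

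**Simulation** (4000 studies per row, equal hazards, nominal 5%):

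| Entry months | Close 32: shift, false positives | Close 44: shift, false positives |
|---|---|---|
| All 0–20 | 0.000, 4.9% | 0.000, 5.1% |
| STEMI 0–12, others 0–20 | −0.006, 9.4% | −0.004, 7.4% |
| STEMI 0–8, others 0–20 | −0.008, 15.2% | −0.006, 11.6% |
| NSTEMI 0–12, others 0–20 | +0.007, 10.2% | +0.005, 8.6% |
| NSTEMI 0–12, STEMI 0–20, controls 20–24 | +0.012, 17.5% | +0.008, 12.6% |
| STEMI 0–12, NSTEMI 0–20, controls 20–24 | −0.003, 6.2% | −0.002, 5.5% |
| Only controls late (20–24) | +0.004, 6.2% | +0.002, 5.3% |

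The earlier closing date, month 26, gives the upper end of the range (0.017, with false positives somewhat above 20%). Late controls partly offset the shift when STEMI closes first and add to it when NSTEMI closes first.

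**With a real difference.** Assume hazards per year of 0.12 (types 1a, 1b), 0.06 (1c/1d), 0.08 (other NSTEMI) and 0.03 (controls), closing at month 32. With a common entry window the difference is 0.031 and power is 82%. With STEMI closing first and controls entering over months 0–20, it falls to 0.020–0.024 and power to 51–64%. With NSTEMI closing first it rises to 0.039–0.043.

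**With a fixed horizon** of 8, 12 or 24 months, equal hazards give a difference of 0.000 and 4.6–5.2% false positives. Under the unequal hazards the mean stays at 0.030–0.031.

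**The case against.** Several objections carry weight.

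- **A reader might infer that 20 months of staggered entry is itself the problem.** It is not: with the same entry window in all groups the paired difference is 0.000.
- **A reader might set a single-marker AUC beside the planned 0.07.** With STEMI entering over months 0–10, NSTEMI over 0–20, 5% mortality per year and closing at month 32, deaths are 10.6% and 8.7%. Cohort membership alone then has sensitivity 10.6/19.3 = 0.549, specificity 91.3/180.7 = 0.505 and AUC 0.527. But 0.07 is a difference between two approaches in the same patients, who are mostly classified alike, so most of this distortion cancels.
- **Unequal closing is inferred.** The documents give one completion date for both MI groups and contradictory signals on order, so neither the occurrence nor the sign of the bias is established.
- **Late selection of controls need not mean late index admission.** They come from a random list and may share the MI groups' calendar period. Late controls alone matter little in any case.
- **A follow-up rule may exist in text not shown.** The visible section numbering runs from 2 to 4, and the data collection list names only in-hospital mortality, so how long-term deaths are ascertained is not visible either.

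What remains is that the ROC method, as stated, has no horizon. A minimum follow-up defined elsewhere would not cure this unless deaths were also cut off at a common time for the ROC.

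**Conclusion.** The point holds as a conditional bias of modest size. If the MI groups close at different times and deaths are counted to one closing date, the paired AUC difference shifts by about 0.005–0.017, in a direction that depends on which group closes first, and false positives rise from 5% to roughly 8–23%. The mildest combinations (late closing, or STEMI first with late controls) fall just below these ranges. The figures rest on the assumed class mix, equal mortality of 8% per year and closing at month 26–44.

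The documents do not support the stronger reading that unequal follow-up could generate the planned 0.07 difference. It could create or mask statistical significance. The Kaplan–Meier, log-rank and Cox analyses allow for unequal follow-up, and the ROC for ACO does not depend on it, so the concern is confined to the mortality ROC. The change is worth making because it is cheap and removes the dependence on closing order.

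**What to change.** In the Statistical Analysis section, define the mortality outcome for the ROC as death within one fixed time from index admission that every patient, including controls, can complete. Alternatively, specify censoring-adjusted time-dependent sensitivity, specificity and AUC at that horizon (Kaplan–Meier or inverse-probability-of-censoring weighted). Compare the two approaches on that measure, in both the unweighted and the admission-weighted analyses. If a common per-patient horizon is already defined elsewhere, one sentence applying it to the ROC is enough.

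The cost is one derived variable or one time-dependent ROC routine, and no new patients. Deaths after the horizon leave the ROC and count only in the survival analyses. A short horizon loses power: under the unequal hazards above, power is 43% at 8 months, 58% at 12 and 85% at 24. The horizon should therefore be the longest that all patients can complete, fixed without reference to the results.
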